## Clinical Experience

Two phase III global randomized studies have evaluated the efficacy of regorafenib. The CORRECT (Patients with metastatic colorectal cancer treated with regorafenib or placebo after failure of standard therapy) trial is an international, multicenter, randomized, double-blind, placebo-controlled study that enrolled 760 patients with mCRC whose disease had progressed after approved standard therapies. Metastatic colorectal cancer patients were randomized to regorafenib plus best supportive care (BSC) or placebo plus BSC. Treatment cycles consisted of 160 mg of regorafenib (or matching placebo) once daily for three weeks on / one week off plus BSC. The primary endpoint of this trial was overall survival. Secondary endpoints included

progression-free survival, objective tumor response rate and disease control rate. The safety and tolerability of the two treatment groups were also compared.

At a preplanned second interim analysis, there was a statistically significant survival benefit for regorafenib. The estimated hazard ratio for overall survival was 0.773 (95% confidence interval [CI], 0.635 to 0.941; 1-sided  $p = .0051$ ). Patients treated with regorafenib had a median overall survival of 6.4 months, compared with 5.0 months for placebo — a 29% increase in survival. In addition to improved overall survival, progression-free survival was superior; median progression-free survival was 1.9 months (95% CI, 1.88 to 2.17) for regorafenib and 1.7 months (95% CI, 1.68 to 1.74) for placebo. The estimated hazard ratio for progression-free survival was 0.493 (95% CI, 0.418 to 0.581; 1-sided  $p < .000001$ ). There was a substantial difference in disease control rate in the regorafenib and placebo groups (44% vs. 15%;  $p < .000001$ ).

Regorafenib demonstrated comparable efficacy benefits across patient subgroups analyzed including age, number of mets, number of lines of prior therapy, and kras status.

The most frequent grade 3+ adverse events in the regorafenib (versus placebo) group were hand-foot skin reaction (17%), fatigue (15%), diarrhea (8%), hyperbilirubinemia (8%), and hypertension (7%). The efficacy and safety results from the CORRECT study supported FDA approval in September 2012.

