## 4. Study Design

Given 54% grade 3/4 toxicity and required dose modification among 76% of patients in the regorafenib arm (randomized phase III CORRECT trial), we will initiate treatment at a reduced dose of 120mg in this geriatric study population on a similar 3 weeks on/1 week off schedule. Dose escalation to 160mg will be recommended after the first cycle (4 weeks) at the discretion of the treating physician. There is good precedent for starting at reduced doses in similar trials – the FOCUS2 study team utilized 80% starting chemotherapy doses in their study among the elderly with metastatic CRC and dose escalated if tolerated.

Participants will undergo a comprehensive geriatric assessment (CGA) at baseline, at 4 weeks and then every 3 months (+/- 7 days) while on study to assess for any deterioration in geriatric domains (functional status, comorbidities, nutrition, psychological state, social support and cognitive ability). All sites have personnel experienced in performing geriatric assessments and the University of Rochester as the lead site will conduct training to ensure that all sites will conduct the assessments in the same way.

All patients will receive intensive one-on-one education about prevention/management of skin toxicity, diarrhea, fatigue and other toxicities at initiation and follow-up visits (see section 7 & 8 for review of treatment strategies). Starter packs with moisturizing cream (10% urea content), socks and patient-friendly ‘Tips for Skin Care’ will be distributed. On-treatment visits will occur weekly for first two cycles and every 4 weeks after that. Alternate weekly visits may be substituted with a home nursing visit for BP check and symptom evaluation if it is not feasible for patient to attend clinic visits weekly. Pill adherence diaries will be provided to patients and pill counts will be performed at the end of every cycle.

Restaging CT/MRI scans will be completed every 12 weeks (+/- 7 days) (or sooner if treating oncologists suspects progression of disease based on clinical symptoms). Radiographic disease progression is defined by Response Evaluation Criteria in Solid Tumors (RECIST 1.1) (see Appendix A). Subjects will have a Safety Follow-up visit within 30 days after their last dose of study drug or prior to the initiation of another antineoplastic therapy, whichever occurs first. After treatment discontinuation, survival status will be assessed periodically (see Table of Assessments).

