### Study Treatment

The initial screening period is 14 days from the date of consent. Once approved, by the coordinating site, an additional 14 day period is granted for scheduling, in which subjects must start treatment.

Regorafenib will be administered as monotherapy during the study. 120 mg qd (starting dose) will be administered for 3 weeks on /1 week off. One cycle is 28 days. Study treatment must be initiated within 14 days of registration.

Three 40-mg regorafenib tablets (starting dose) should be taken once a day with approximately 8 fluid ounces (240 mL) of water after a low-fat (<30% fat) meal. Some examples of low fat meals are:

- Two slices of white toast with 1 tablespoon of low-fat margarine and 1 tablespoon of jelly and 8 ounces (240 mL) of skim milk (approximately 319 calories and 8.2 g of fat).
- One cup of cereal (i.e. Special K), 8 ounces (240 mL) of skim milk, one piece of toast with jam (no butter or marmalade), apple juice, and one cup of coffee or tea (2 g fat, 17 g protein, 93 g of carbohydrate, 520 calories).

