- f Comprehensive geriatric assessment (CGA) will be performed at baseline, at 4 weeks, and then every 12 weeks during the study protocol (+/- 7 days). The baseline CGA can be performed at the week 1 visit prior to dispensing Regorafenib. These questionnaires can be completed at the study visit or given to the patient to take home, complete, and send back, or mailed to the patient to be completed prior to the next visit.
- g CMP to include Sodium (Na), Potassium (K), Chloride (Cl), Bicarbonate (HCO3), Blood Urea Nitrogen (BUN), Creatinine (Cr), Glucose, Calcium (Ca), Magnesium (Mg), Total Protein, Albumin, Alkaline Phosphatase, Total Bilirubin, Alanine Aminotransferase (ALT) and Aspartate Aminotransferase (AST).
- h Pre-study imaging must have been completed within 30 days prior to registration. Restaging imaging will be performed every 12 weeks (+/- 7 days) when patients are on protocol treatment until disease progression and is defined by Response Evaluation Criteria in Solid Tumors (RECIST 1.1)
- i Treatment will be given 3 weeks on/1 week off and will continue until disease progression or other reason for discontinuation of protocol treatment.
- j Lab work is required every 4 weeks after cycle 4 as long as patient remains on study
- k Initial screening period is 14 days from the date of consent. Once approved, by the coordinating site, an additional 14 day period is granted for scheduling, in which subjects must start treatment
- l Pre study labs can be used for week 1.

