## 18. Appendices

### Appendix A – RECIST 1.1 Criteria

	RECIST 1.1
Measurable Disease: Tumor Lesions	
Tumor lesions must be accurately measured in at least one dimension (longest diameter in the plane of measurement is to be recorded with a minimum size of):
 
 
- 10mm by CT /MRI scan (scan slice thickness no greater than 5mm)
 
- 10mm caliper measurement by clinical exam (lesions which cannot be accurately measured with calipers should be recorded as non-measurable)
 
- 20mm by chest X-ray
 

Measurable Disease: Malignant Lymph Node	
Sum of the diameters (longest for non-nodal lesions, short axis for nodal lesions)
 
Measure SHORT axis:
 
 
- Target lesion if short axis <math>\geq 1.5</math>cm
 
- Non-target if short axis 1.0 to <math><1.5</math>cm or pathological
 
- Normal lymph node if short axis <math>< 1.0</math>cm
 
 
Add ACTUAL short axis measurement to sum of longest diameters of non-nodal lesions.

Target Lesions	
All measurable lesions:
 
 
- Up to 5 target lesions max in total
 
- Up to 2 target lesions max per organ
 

Non-Target Lesions	
All other lesions (site of disease). Measurements are not required and these lesions should be followed as:
 
 
- Present
 
- Absent
 
- Unequivocal progression
 

New Lesions	
The appearance of new malignant lesions denotes disease progression.

Methods for Evaluation of Measurable Disease	
All measurements should be taken and recorded in metric notation, using a ruler, calipers, or digital measurement tool. All baseline evaluations should be performed as closely as possible to the beginning of treatment and never more than 4 weeks before the beginning of the treatment. The same method of assessment and the same technique should be used to characterize each identified and reported lesion at baseline and during follow-up. Imaging-based evaluation should always be done rather than clinical examination unless the lesion(s) being followed cannot be imaged but are assessable by clinical exam.

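### Baseline scan may be 44 days old at first dose against a 4-week limit; PFS and OS start at a randomization that never occurs; median PFS can depend on the 12-week scan calendar

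*Combined protocol and SAP*

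**What the plan says.** **Baseline scan.** Footnote h of the Table of Assessments (Timing of assessments) states "Pre-study imaging must have been completed within 30 days prior to registration". Section 7 (Study Treatment) adds "Study treatment must be initiated within 14 days of registration", and footnote k agrees: "an additional 14 day period is granted for scheduling, in which subjects must start treatment". Appendix A, which Section 4 and the Efficacy text cite for progression and response, requires baseline evaluations "never more than 4 weeks before the beginning of the treatment".

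**Time origin.** Section 10 (Efficacy) measures both PFS and OS from the date of randomization. The Synopsis describes a single-arm, open-label study with historical control.

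**Restaging.** Section 4 says "Restaging CT/MRI scans will be completed every 12 weeks (+/- 7 days) (or sooner if treating oncologists suspects progression of disease"; footnote h has the same 12-week interval while patients are on treatment. Neither says which date the 12 weeks are counted from. Section 4 also says "On-treatment visits will occur weekly for first two cycles and every 4 weeks after that". Once a patient stops treatment without progression, scan frequency is left to the treating physician (Follow-up Period).

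**Analysis.** Section 12 plans Kaplan-Meier curves and a median for PFS and OS, with no rule for dating progression between scans. The only regorafenib PFS reference is from CORRECT (Section 1, Clinical Experience): "median progression-free survival was 1.9 months (95% CI, 1.88 to 2.17) for regorafenib and 1.7 months".

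**The concern.** The baseline scan is the reference for every later RECIST call. If it is older than the response criteria allow, tumour growth before treatment can count as change on treatment and enter the response rate, disease control rate and PFS. Two rules in one protocol give different limits, and nothing says which prevails.

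A survival time needs a start date. The one named does not exist here, so sites or analysts could choose consent, registration or first dose.

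Finally, progression without symptoms is seen only when a scan is done. If the first scheduled scan comes well after the time by which half of patients have progressed, the estimated median tends towards the scan date. With a historical control, readers are likely to set that median beside 1.9 months.

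**Working it through.** **1. Age of the baseline scan**

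- Longest permitted gap: 30 days (footnote h) + 14 days (Section 7, footnote k) = 44 days.
- Appendix A limit: 4 weeks = 28 days. Excess: 44 - 28 = 16 days.
- Dosed on the day of registration: 30 - 28 = 2 days over.
- Longest span from baseline to first scheduled restaging, counted from first dose: 44 + 91 = 135 days, against 28 + 91 = 119 under Appendix A.
- If Appendix A governs, the 30-day limit never binds: a scan at most 28 days before first dose is at most 28 days before registration.

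**2. Time origin**

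Registration and first dose can differ by 14 days. The CORRECT median is 1.9 x 30.44 = 57.8 days (8.3 weeks), so the choice between them can move an individual PFS time by up to 14/57.8 = 24% of that median.

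**3. Scan calendar**

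Assume the 12 weeks run from first dose. The first scheduled scan is then at 84 ± 7 days, i.e. days 77-91 (weeks 11-13). With exponential PFS and a true median of 1.9 months, the share with an event by day t is 1 - 0.5^(t/57.8): 60% at day 77, 63% at day 84, 66% at day 91. For the median to fall before day 77, about 0.5/0.603 = 83% of those early events must be dated off the schedule, through death or a symptom-prompted scan.

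Simulation assumptions: n = 60; 4,000 trials; scans every 12 weeks ± 1 week; symptom-found progressions dated at onset; deaths dated exactly with median OS 6.4 months (CORRECT). Ranges span two death models, with 17% or 26% dead by week 12.

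| Progressions found through symptoms | KM median, true 1.9 mo | Trials with that median in weeks 11-13 | KM median, true 3.45 mo |
|---|---|---|---|
| 0% | 2.82-2.85 | 99% | 3.87-4.94 |
| 50% | 2.67-2.72 | 86-96% | 3.54-3.84 |
| 75% | 2.38-2.54 | 38-52% | 3.44-3.55 |
| 90% | 2.03-2.08 | 12-14% | 3.40-3.42 |
| 100% | 1.86-1.87 | 4% | 3.37-3.38 |

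The 3.45 months is 1.7/0.493, the CORRECT placebo median divided by the PFS hazard ratio. There the median falls inside weeks 11-13 in only 15-24% of trials, although with no symptom pick-up it is still later than the truth. With a true median of 1.9 months and at most half found through symptoms, Weibull shapes from 0.7 to 2 also give about 2.6-2.9 months.

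**4. A summary that does not move with pick-up**

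By each patient's first scheduled scan, every earlier progression has been recorded, whichever way it was found. With a true median of 1.9 months the proportion progression-free at that scan is 36-37% at every pick-up share (1 - 0.635 = 0.365). For 22/60 the exact 95% CI is 24.6-50.1%. The Kaplan-Meier curve read at a fixed date lacks this property: at 50% pick-up it gives 58-63% at week 11, 46-49% at week 12 and 35% at week 13.

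**The case against.** **On the baseline scan.** A site can meet both limits by using the stricter one, and Section 14 demands strict adherence to every specification. The excess is 2 days with same-day dosing and reaches 16 only when both windows are used in full. This bears on size, and 44 days should not be read as typical. It does not remove the conflict: no text says which limit prevails, and a scan that footnote h accepts can be one that Appendix A rules out.

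**On the scan calendar.** A Kaplan-Meier median with periodic scans is ordinary practice; symptom-prompted scans are allowed, visits are weekly for two cycles, and no test, decision rule or sample size uses PFS. An exponential curve with median 1.9 months also fits CORRECT poorly: medians of 1.9 and 1.7 would imply a hazard ratio of 1.7/1.9 = 0.89, not 0.493. The population differs too. All of this stands, and it is why the third point is an improvement and not an error.

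**Stronger readings to avoid.** A reader might infer that this trial's median PFS will be too long relative to CORRECT. The documents do not give CORRECT's scan interval, so no direction can be claimed. A reader might also infer that an interval-censored analysis would recover the true median. An exponential fit does so only if PFS is exponential. With the true median held at 1.9 months, it gave 2.8-3.0 at Weibull shape 0.7, about 1.5 at shape 1.5 and 1.3-1.4 at shape 2, so it can do worse than the planned median.

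**Conclusion.** Two items are wrong as written. Footnote h with the 14-day start window permits a baseline scan 44 days before first dose, against 28 in Appendix A; this follows from the text alone. PFS and OS have a start date that does not occur in this design. The effect of the older scan on response rate, disease control rate and PFS cannot be sized from the documents.

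The third item holds only conditionally. It needs a true median near 1.9 months, half or fewer of progressions found through symptoms, and restaging counted from first dose. The documents give neither the pick-up share nor the anchor. Under those conditions the Kaplan-Meier median mostly reports when the first scan took place. With high pick-up, or a true median near 3.45 months, it does not.

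All the efficacy endpoints concerned are secondary and descriptive. The primary toxicity endpoint and the sample size are untouched, and the scan schedule does not affect OS. The first two items should be corrected; the third is worth adding because it costs little.

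**What to change.** 1. **Reconcile footnote h with Appendix A** by anchoring the baseline imaging window to first dose, within the 4 weeks Appendix A already states. Cost: one footnote and an occasional repeat baseline scan. With the 14-day start window kept, only scans more than 14 days old at registration are at risk (14 + 14 = 28).
2. **Time PFS and OS from first dose** in Section 10, and say that the 12-week restaging interval runs from the same date. Cost: two sentences.
3. **Keep the Kaplan-Meier curves and median, and add** the proportion alive and progression-free at the first scheduled restaging, with an exact 95% CI, taken from each patient's own scan. Earlier progressions and deaths are events. Patients who stop without progression and have no scan count as not progression-free, with the opposite count reported as a bound. Fix this rule in advance, because it matters: if 3, 6 or 12 of 60 are unscanned and 36.5% of the rest are progression-free, the two counts give 21/60 to 24/60 (35-40%), 20/60 to 26/60 (33-43%) or 18/60 to 30/60 (30-50%).
4. **State in Section 12** that median PFS and disease control rate depend on the scan schedule, so any comparison with historical figures must take account of it.

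Items 3 and 4 need a little extra analysis and no extra scans.

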### Dose Modification Levels

The starting dose of regorafenib is 120 mg once daily. Study medication will be administered on a 3 weeks on/1 week off schedule [3 weeks out of every 4].

Dose escalation to 160mg is recommended after the first cycle (4 weeks) at the discretion of the treating physician.

Doses will be held or reduced for clinically significant hematologic and non-hematologic toxicities that are related to protocol therapy according to the guidelines shown in the Dose Delays/Dose Modifications tables that follow. Doses held for toxicity will not be made up but will be counted as missed doses. Dose modifications will follow predefined dose levels. Sites may also follow their institutional practice for dose modifications. Missed doses are to be omitted rather than made up. Dose adjustments for hematologic toxicity are based on the blood counts obtained in preparation for the day of treatment.

The modifications of regorafenib will follow the following predefined dose levels:		
Dose level +1	160mg po qd	Four 40-mg tablets of regorafenib
Dose level 0 (starting dose)	120 mg po qd	Three 40-mg tablets of regorafenib
Dose level - 1	80 mg po qd	Two 40-mg tablets of regorafenib
Dose level - 2	40 mg po qd	One 40-mg tablets of regorafenib

If a subject experiences more than one toxicity, dose reduction should be according to the toxicity with the highest grade.

In the case of two or more toxicities of the same grade, the investigator may dose reduce according to that deemed most causally related to study treatment.

If a dose reduction has been performed, intra-subject dose re-escalation can be considered (up to the maximal 160 mg daily dose) at the discretion of the treating physician provided that the toxicity(ies) has resolved to baseline.

The following tables outline dose adjustments for toxicities related to study drug other than diarrhea, hand-foot skin reaction, hypertension and liver function test abnormalities. More information on dose reductions for diarrhea, hand-foot skin reaction, hypertension, and liver function test abnormalities follows Table 7-1.

Table 7-1: Recommended dose modification for toxicities except diarrhea, hand-foot-skin reaction, hypertension and ALT/ST/bilirubin			
NCI-CTCAE v4.0a	Dose Interruption	Dose Modificationb	Dose for Subsequent Cycles
Grade 0-1	Treat on time	No change	No change
Grade 2 c	Treat on time	No change	No change

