## **Timing of assessments**

See Table of Assessments

Study Day a	PRE STUDY k	Cycle 1				Cycle 2				Cycle 3				Cycle 4				FU Prior to Progression c	Safety FU 30 days after last treatment dose	FU After Progression d
		W	W	W	W	W	W	W	W	W	W	W	W	W	W	W b				
REQUIRED STUDIES																				
PHYSICAL																				
History and Physical Exam e	X	X	X	X	X	X	X	X	X	X	X	X	X	X	X	X	X	X	X	
Weight and Performance Status e	X	X	X	X	X	X	X	X	X	X	X	X	X	X	X	X	X	X	X	
Blood Pressure e	X	X	X	X	X	X	X	X	X	X	X	X	X	X	X	X	X	X	X	
Disease Assessment	X																			
Toxicity Evaluation/Support e		X	X	X	X	X	X	X	X	X	X	X	X	X	X	X	X	X	X	
Comprehensive Geriatric Assessment f	X				X															
Pill count					X															
LABORATORYl																				
CBC/Differential	X	X	X	X	X	X	X	X	X	X	X	X	X	X	X	X	X	X 	X	
Comprehensive Metabolic Panel g	X	X	X	X	X	X	X	X	X	X	X	X	X	X	X	X	X	X 	X	
- Phosphorus	X	X	X	X	X	X	X	X	X	X	X	X	X	X	X	X	X	X 	X	
INR	X	X	X	X	X	X	X	X	X	X	X	X	X	X	X	X	X	X	X	
aPTT	X	X	X	X	X	X	X	X	X	X	X	X	X	X	X	X	X	X	X	
SCANS																				
CT/MRI of Chest h	X																		X	
CT/MRI of Abdomen and Pelvis h	X																		X	
TREATMENT																				
Regorafenib i		X	X	X	X	X	X	X	X	X	X	X	X	X	X	X	X	X	X	

- a Except for week 1 visit, there is a window of +/- 5 days for subsequent follow up visits.
- b Patients with stable disease and on protocol treatment beyond cycle 4 will be followed every 4 weeks until disease progression.
- c Patients off protocol treatment secondary to reasons other than progression will have physical exams performed at least every 3 months or earlier as clinically indicated until closure of the study. Frequency of radiographic studies will be determined by the treating physicians.
- d After disease progression subsequent anti-neoplastic therapy and survival status will be assessed every 6 months for the remainder of the study or until death.
- e Alternate weekly visits may be substituted with a home visit or phone call for BP check and symptom evaluation if it is not feasible for patients to attend clinic visits weekly.

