#### **Assessments and documentation of adverse events**

Adverse events and grade will be recorded at each follow-up visit. Serious adverse events will be collected and reported from the time patient signs informed consent until the End of Treatment safety follow-up visit. Non-serious adverse events will be collected from the time of first study drug dosing until the End of Treatment safety follow-up visit.

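### The Table of Assessments lets pre-study labs of any age replace the week 1 panel, so laboratory worsening before the first dose can be counted in the grade 3-5 rate

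*Combined protocol and SAP*

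**What the plan says.** The Table of Assessments (Section 10, Timing of assessments) marks blood count, metabolic panel, phosphorus, INR and aPTT at the pre-study visit, at week 1 and at the weekly visits that follow. Footnote l then relaxes week 1: "Pre study labs can be used for week 1". It states no maximum age for those labs. Footnote h, by contrast, does limit the age of pre-study imaging, to 30 days before registration.

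Section 7 (Study Treatment) sets the time available: "The initial screening period is 14 days from the date of consent", after which "an additional 14 day period is granted for scheduling, in which subjects must start treatment". Footnote k repeats both windows, and Section 7 also says "Study treatment must be initiated within 14 days of registration". For visits after the first, footnote a says "Except for week 1 visit, there is a window of +/- 5 days for subsequent follow up visits".

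Four other places bear on how a laboratory event is counted:

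- Section 11 (Definitions) includes abnormal laboratory findings among adverse events.
- Section 11 (Assessments and documentation of adverse events) says "Non-serious adverse events will be collected from the time of first study drug dosing".
- Section 12 makes the incidence of grade 3-5 toxicity the primary endpoint. It does not define a laboratory baseline, a treatment-emergent event or a restriction by causality.
- Section 10 (Prior and concomitant therapy) requires liver tests before regorafenib is started, but does not say how long before.

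**The concern.** In a single-arm study, only timing and the investigator's judgement separate the effect of the drug from the course of the disease. Timing needs a measurement close to the first dose. Footnote l allows that measurement to be skipped, in patients who under the exclusion criteria have had no systemic therapy for metastatic disease for at least 28 days before starting.

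A laboratory value that crosses into grade 3 after the screening sample but before dosing would first be seen at week 2. By then it falls inside the collection period and looks like an on-treatment event. Counting it would raise the primary rate, which works against the plan's hypothesis that a lower starting dose and supportive care reduce toxicity.

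Laboratory events are a real part of this endpoint. Section 1 lists hyperbilirubinemia (8%) among the most frequent grade 3 or higher events in the CORRECT regorafenib arm. The exposure is probably greatest for transaminases in patients with liver involvement. They may enter at up to 5 x ULN, directly below the row of Table 8-4 that starts above 5 x ULN, so a small drift before dosing can cross that line.

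**Working it through.** **The plan's own interval.** Section 12 gives 60 patients, an expected rate of 45% and a 90% CI of 0.341 to 0.564. With 0.45 x 60 = 27 events, the exact (Clopper-Pearson) 90% CI for 27/60 is 0.340 to 0.564, which agrees to 0.001. It serves here only as a scale.

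**Age of the labs at first dose.** Screening window 14 days + scheduling window 14 days = 28 days. This maximum assumes that the sample is taken on the day of consent and that both windows are used in full. The documents do not state the figure; it follows from the windows. Routine-care labs taken before consent are not clearly barred, so an older sample is possible.

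**Interval between the two samples.** Take the first dose as day 1 and week 2 as nominal day 8, with 5 days either way. The interval is 28 + (d - 1) days, where d is the day of the week 2 sample.

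| Week 2 sample | Interval (days) | Share before first dose |
|---|---|---|
| Day 3 | 28 + 2 = 30 | 28/30 = 93% |
| Day 8 | 28 + 7 = 35 | 28/35 = 80% |
| Day 13 | 28 + 12 = 40 | 28/40 = 70% |

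At the maximum, most of the time in which a change could have arisen lies before treatment.

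**Whether the plan removes such an event.** Three possible routes were checked.

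- A baseline or treatment-emergent rule: none in Section 11 or Section 12.
- A required sample near the first dose: the liver-test requirement has no time limit, so the screening sample satisfies it.
- Causality: the investigator answers yes or no for every event, but Section 11 reports events whether or not they are drug-related, and Section 12 does not say that the primary rate is limited to related events.

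The third route is open but not assured.

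**Effect on the rate.** One patient is 1/60 = 1.7 points, if that patient has no other grade 3-5 event. The number affected is not in the documents, so the values below are illustrations.

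| Patients added (assumed) | Rate | Exact 90% CI |
|---|---|---|
| 0 | 27/60 = 45.0% | 0.340 to 0.564 |
| 1 | 28/60 = 46.7% | 0.356 to 0.580 |
| 3 | 30/60 = 50.0% | 0.387 to 0.613 |
| 6 | 33/60 = 55.0% | 0.436 to 0.660 |

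Some affected patients would be counted anyway for another event. If the two are independent and the rate is 45%, an affected patient is newly counted with probability 0.55 and adds 0.55/60 = 0.9 points on average.

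**The case against.** The strongest reply is that several things must coincide. A site must choose to use footnote l, which is a permission and not an instruction. The sample must be early and the start late. The worsening must reach grade 3 and must escape the history, examination, performance status and toxicity evaluation that remain scheduled at week 1. The objective concerns toxicity of regorafenib, and the causality section accepts a clear alternative explanation as grounds for answering no. Section 8 (Liver Function Abnormalities) names disease progression as such an alternative for liver tests. All of this stands, and it limits both how certain and how large the effect is. It does not close the gap: the primary endpoint is not stated to be limited to related events, and without a recent pre-dose value the investigator has little evidence for answering no.

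A further reply is that the missing baseline rule in Section 12 is the root of the problem, and that a fresh week 1 panel alone would not remove an abnormality already present. That is correct, and the fix therefore needs both parts.

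A reader might infer stronger claims that the documents do not support:

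- *Such events will be counted.* No sentence says so. The text supports only that they can be.
- *No pre-dose value exists.* One does, from the eligibility labs. It may be old, but it is not absent.
- *Footnote l contradicts Section 7, which says "Dose adjustments for hematologic toxicity are based on the blood counts obtained in preparation for the day of treatment".* That sentence governs dose adjustment for hematologic toxicity, not the first dose, so the two do not conflict.
- *The bias can be sized from the CORRECT placebo median PFS of 1.7 months.* This would also need the share of progressing patients who reach a new grade 3 laboratory value, which the documents do not give. It would treat progression or death as a stand-in for laboratory failure, place every patient at the maximum gap and ignore patients already counted.

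**Conclusion.** The point holds in a limited form. Footnote l permits laboratory values up to 28 days old to serve at the first dose, and nothing in Sections 11 or 12 reliably keeps worsening before dosing out of the grade 3-5 rate. The error can only push that rate upward. It is confined to laboratory events of grade 3 or higher, at sites that use the permission, and it disappears for a given patient if the event is judged unrelated and only related events are counted.

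The size cannot be derived from the documents. Each newly counted patient moves the rate by 1.7 points, and the total is probably small against the margin of about 12 points stated in Section 12. That judgement assumes that few patients are affected. The change is worth making because it is cheap and because a pre-dose value that was not taken cannot be recovered at analysis. It does not threaten the trial's main result.

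**What to change.** Two linked changes:

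1. **Table of Assessments, footnote l.** Allow pre-study labs to stand for week 1 only if they were taken within a stated short window before the first dose. Otherwise perform the week 1 panel already in the table, before dosing. Seven days is a common convention, but the documents do not supply a figure and the sponsor may set another.
2. **Section 12.** Define the laboratory baseline as the last value before the first dose. Count a laboratory grade 3-5 event in the primary endpoint only if it is new or of a worse grade than that baseline. In the same place, state whether the primary rate covers all events or only those judged related.

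The cost is one blood draw for patients whose screening labs are older than the window, plus short edits to the footnote and to Section 12. No new visit is needed, and neither the sample size nor the planned form of analysis changes.
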